2 PROTOCOL SYNOPSIS

Protocol Title: A Phase 2 Multi-Center, Open Label Study to Assess the Safety, Efficacy and Pharmacodynamics of IMG-7289 in Patients with Essential Thrombocythemia

Protocol No: IMG-7289-CTP-201

Sites: Approximately 25 sites in Australia, Italy, Germany, New Zealand, UK and US with additional sites and countries as needed.

Study Objectives:

Hypothesis: IMG-7289 is a safe and tolerable orally available agent when administered to patients with essential thrombocythemia; inhibition of LSD1 by IMG-7289 will reduce both the number of megakaryocytes and their capacity to secrete growth factors and inflammatory cytokines to the clinical benefit of patients with ET.

Primary Objectives: To evaluate in ET patients the effect of IMG-7289 on:

- Safety and tolerability
- Reduction of platelet counts to ≤ 400 k/ μ L (400×10^9 /L) in the absence of new thromboembolic events

CCI

Investigational Drug: The active drug substance is identified as IMG-7289(bomedemstat). IMG-7289 is an irreversible inhibitor of LSD1. The chemical name is: *N*-[[(2*S*)-5-[[[(1*R*, 2*S*)-2-(4-fluorophenyl) cyclopropyl]amino]-1-(4- methylpiperazin-1-yl)-1-oxopentan-2-yl]-4-(1*H*-1,2,3-triazol-1-yl)]benzamide, bis-tosylate salt.

IMG-7289 will be supplied as capsules in multiple strengths. These strengths, based on IMG-7289 free base, i.e., the active substance, may include: 5 mg, 10 mg, 25 mg and 50 mg. Capsule strengths provided may change throughout the duration of the study. Such details will be included *via* updates to the Pharmacy Manual.

Study Population: Approximately 60 patients eighteen years of age or older in a population of ET patients requiring platelet control that have failed at least one standard therapy (failure is the equivalent of inadequate response or intolerance).

Methodology: This is a Phase 2 multi-center, open-label study evaluating the safety, efficacy and pharmacodynamics of IMG-7289 administered orally once daily in patients with essential thrombocythemia (ET).

Preclinical testing of LSD1 inhibition in mouse models of myeloproliferative neoplasm induced apoptosis in mutant stem/progenitor cells, reduced inflammatory cytokines, reduced spleen length and weight, decreased bone marrow fibrosis if present, and reduced extramedullary hematopoiesis. Additionally, LSD1 inhibition with IMG-7289 was shown in a *Jak2^{V617F}* mouse model of ET/polycythemia vera (PV) to selectively decrease the number of malignant megakaryocytes as well as reduce elevated platelets, red cells and granulocytes (Jutzi *et al.*, 2018). To date, IMG-7289 has been investigated in patients with acute myeloid leukemia, myelodysplastic syndrome and myelofibrosis patients, with notable changes in the myelofibrosis population including dose-dependent decreases in IL-8, platelets, and neutrophils.

The therapeutic goal for the treatment of ET is to inhibit the activity of LSD1 in hematopoietic cells for only a *fraction* of the 24-hour dosing cycle, sufficient to reduce the production of platelets whose over-production characterizes this condition. Considerations leading to the choice of a safe starting dose include chronic toxicology studies in conjunction with the clinical experience of the eighty-five patients who have received IMG-7289 to date. Using all available information in conjunction with the therapeutic goal for the treatment of ET, the starting dose of IMG-7289 of 0.6 mg/kg QD has been selected. Refer to Section 3.6 for additional detail on the rationale for the starting dose and dose regimen.

To ensure patient safety, a Safety Advisory Board (SAB) will perform reviews at least quarterly of safety parameters and pharmacodynamic markers to draw conclusions around the safety and pharmacodynamic effect of IMG-7289. The SAB will also review patient dose titrations and may recommend adjustments.

Study Conduct: This study consists of two treatment periods: the Initial Treatment Period (ITP), followed by the Additional Treatment Period (ATP). In the ITP, patients will be treated daily for 169 days. The ATP offers treatment to qualifying patients for an additional 169 days.

During the ITP, patients will initially return for study assessments every other week (bi-weekly) for the first 12 weeks (ITP Days 15, 29, 43, 57, 71 and 85) and then monthly for 12 weeks (ITP Days 113, 141 and 169). It is anticipated that by Week 12 (Day 85) the great majority of patients will have achieved a stable dose. For safety purposes, bi-weekly visits may continue at the PI's discretion post Day 85 if necessary. On Day 169, bone marrow sampling is also required. Additionally, at the Day 169 visit a 'qualification' assessment will be made to determine whether the patient is deriving clinical benefit (defined as not meeting "progressive disease" criteria as per Appendix 16.5) and safely tolerating IMG-7289. For the patients who qualify for entry into

the ATP, transition should occur without interruption in dosing. Patients not deriving clinical benefit will discontinue IMG-7289 and undergo End of Treatment (EoT), pre-End of Study (pre-EoS) and End of Study (EoS) visits.

In the ATP, treatment may continue for an additional 169 days in those patients deriving clinical benefit, as determined by the Principal Investigator. Qualifying patients will return for study assessments monthly (ATP Days 1, 29, 57, 85, 113, 141 and 169). It is anticipated that patients continuing in the ATP will have already achieved a stable dose, with every other week visits no longer necessary. For safety purposes, every other week visits may continue at the PI's discretion, if necessary. On Day 169 of every other ATP (i.e., ATP 2, ATP 4, etc.), the equivalent of yearly, bone marrow sampling is also required. At the Day 169 visit, a 'qualification' assessment will be made to determine whether the patient is continuing to derive clinical benefit. Such patients thereby qualify for re-entry into the ATP, which is iterative; patients may continue to receive IMG-7289 for as long as they continue to qualify.

Patients will be followed closely throughout the study for both Adverse Events (AEs) and signs of toxicity by frequent monitoring of clinical signs and symptoms as well as safety labs. Pharmacodynamic effects will be closely monitored by frequent hematology assessments of peripheral blood, and requisite bone marrow aspirates and biopsies. Throughout dosing, transfusions may be administered if needed in accordance with standard institutional guidelines.

IMG-7289 Dosing: Through the use of dose titration, the dose of IMG-7289 will be adjusted for each patient to that dose that provides sufficient exposure to safely inhibit thrombopoiesis for a fraction of the dosing cycle (designated as the D_{pi}).

Initial Treatment Period (ITP):

All patients will be treated daily, for up to 169 days of dosing. Treatment will begin on Day 1 at the starting dose (D_s) of 0.6 mg/kg QD. Details on the selection and rationale for the starting dose and dosing schedule can be found in Sections 3.6.1 and 3.6.2. Dose-titration, both upward and downward, is contingent on the hematology assessment and comparison of hematology values from the prior study visit. **Up-titrations** may begin on ITP Day 28 and occur no more frequently than every 4 weeks from the previous up- or down-titration. **Down-titrations** can be made at any time in the best interest of the patient. Up-titrations will be made in increments of 0.2 mg/kg/d, and down-titrations in decrements of 0.1 or 0.15 mg/kg/d.

CCI

CCI

Study Duration: Screening procedures may commence up to 28 days prior to the start of treatment. Patients may initially receive up to 24 weeks of dosing while on-study. Patients will be followed for 14 days post last dose. Therefore, the anticipated duration of participation in the study is expected to be approximately 30 weeks from first patient visit to last patient visit. Additional treatment may be given, contingent on an assessment of patient benefit.

Study Assessments: The assessments outlined below are also summarized in Study Assessments Section 9 and in the Schedule of Assessments Sections 16.1.

The Myeloproliferative Neoplasm Symptom Assessment Form (MPN-SAF; Appendix 16.6) will be completed during Screening (as close to Day -7 as possible), pre-dose Day 1, weekly from Day 7 through the EoS Visit, and upon suspicion of relapse. Multiple questionnaires will need to be provided to the patient at each visit for completion during each 'off week'.

ECOG Performance Status (Appendix 16.4) will be performed at Screening, and on Days 85 and 169 of the ITP, on Day 169 of the ATP for as long as the patient continues to qualify, at EoT, EoS/ET, and upon suspicion of relapse.

Patient Global Impression of Change (PGIC; Appendix 16.7) will be performed at Days 85 and 169 of the ITP, on Day 169 of the ATP for as long as the patient continues to qualify, at EoT, EoS/ET, and upon suspicion of relapse.

Adverse events (AEs) will be assessed at every visit post first dose through the EoS visit.

Note for UK: Non-serious events occurring pre-first IMG-7289 dose will be recorded as Medical History; those occurring post first IMG-7289 dose through the EoS visit will be recorded as AEs. Serious AEs (SAEs) will be recorded from time of consent through the EoS/ET visit or until the Investigator and Imago determine follow-up is no longer necessary.

Physical Examinations (PE): a **Full Physical Exam**, including vital signs, and height will be performed at Screening. **Limited Physical Exams (LPE)**, including vital signs, will be performed on Day 1 and at every study visit throughout the study (noted exception: if patient's dose has not stabilized and more frequent visits than detailed in the visit schedule are deemed necessary, LPEs are not required at these additional visits). CCI

Serum pregnancy testing will be performed for women of child-bearing potential (WOCBP) at Screening, pre- dose Day 1, monthly (i.e., Days 29, 57, 85, 113, 141 and 169) throughout the study, upon suspicion of relapse, at the EoT, pre-EoS, and EoS/ET visits, and if pregnancy is suspected while the patient remains on-study.

Bone marrow aspirate* and biopsy will be performed**:

- At Screening (no more than 28 days prior to the first IMG-7289 dose).
- At Day 169 visit (± 7 days).
- Approximately every 12 months thereafter, at Day 169 (± 7 days) of every other Additional Treatment Period (i.e., ATP 2, ATP 4, etc.), the equivalent of yearly, for as long as the patient continues to qualify.
- At EoT, EoS/ET, and upon suspicion of relapse, unless performed within the prior 5 weeks.

*Aspirate from the first pull whenever possible, but no later than the second, is required (except in case of dry tap).

**The total number of bone marrow evaluations required during the Initial Treatment Period is 2 in ~30 weeks. Additional marrow evaluation is required only if the patient qualifies for the Additional Treatment Period, is suspected to have relapsed after demonstrating response, or upon evidence of progressive disease.

Clinical laboratory measures: The following laboratory measures will be performed at Screening, pre-dose Day 1, then as described below for individual panels, upon suspicion of relapse, and at the EoT, pre-EoS, and EoS/ET visits:

- Hematology with automated differential – at every visit throughout the study
- Chemistry – monthly (i.e., Days 29, 57, 85, 113, 141 and 169) throughout the study
- Coagulation – Days 85 and 169 throughout the study
- Urinalysis – Days 85 and 169 throughout the study
- **Note:** In Italy, HIV, HAV, HBsAg, HBsAb, HBcAb and HCV testing must also be performed at Screening and EoT/ET.

Mutant (variant) allele burden: The following laboratory samples will be collected at the time-points noted:

- Germline samples for genomic analysis - Screening
- Peripheral blood for genomic analysis
 - Screening, Day 169, and at Day 169 of *every* ATP (i.e., ATP 1, ATP 2, etc.) for as long as the patient continues to qualify
 - At EoT, EoS/ET and upon suspicion of relapse*
- Bone marrow for genomic analysis
 - Screening, Day 169, and at Day 169 of *every other* ATP (i.e., ATP 2, ATP 4, etc.), the equivalent of yearly, for as long as the patient continues to qualify
 - At EoT, EoS/ET and upon suspicion of relapse*

*Required at EoT, EoS/ET and upon suspicion of relapse unless performed within the prior 5 weeks.

Future Correlative Studies: Blood will be collected in conjunction with each genomic blood sampling time-point, as detailed above, for the purposes of potential correlative studies

Titration Assessment: At every visit following Day 1 patients will be assessed for dose titrations using the titration and re-challenge rules in **Table 1**.

- Up-titrations are permitted no more frequently than every 4 weeks from the previous up- or down-titration.
- Down-titrations are permitted at any time in the patient's best interest.

Cytokines: Sample collection time-points are below.

- Pre-dose Day 1, Days 15, 29, 57, 85 and 169, and at Day 169 of the ATP for as long as the patient continues to qualify
- At EoT, and at ET (ET required only if the patient discontinues during the ITP)

Qualification Assessments:

- *Initial Treatment Period Day 169:* Assess whether the patient is eligible for the ATP. If it is determined that the patient is deriving clinical benefit and safely tolerating IMG-7289, then the patient qualifies for and may enter the ATP upon completion of the Day 169 visit.
- *Additional Treatment Period Day 169:* Assess whether the patient continues to be eligible for the ATP. Refer to ITP Day 169 above, as the process is the same.

Eligibility Criteria: Patients must meet all applicable Inclusion and none of the Exclusion Criteria.

Inclusion Criteria:

1. Age \geq 18 years.
2. Diagnosis of Essential Thrombocythemia per World Health Organization (WHO) diagnostic criteria for myeloproliferative neoplasms ([Arber et al., 2016](#)).

3. Patients who have failed at least one standard therapy (failure is the equivalent of inadequate response or intolerance). European Leukemia Net (ELN) criteria for intolerance / resistance to hydroxyurea (Appendix 16.8) may be used in association with Investigator discretion. Ruxolitinib refractoriness or intolerance will be left to the discretion of the Investigator.
4. Requires treatment in order to lower platelet counts based on patient age over 60 or history of thrombosis.
5. Platelet count > 450 k/ μ L (450×10^9 /L) pre-dose Day 1.
6. Peripheral blast count < 1% pre-dose Day 1.
7. ANC $\geq 0.5 \times 10^9$ /L pre-dose Day 1.
8. Fibrosis Score < grade 2, as per a slightly modified version ([Arber *et al.*, 2016](#)) of the European Consensus Criteria for Grading Myelofibrosis ([Thiele *et al.*, 2005](#)).
9. Life expectancy > 36 weeks.
10. Able to swallow capsules.
11. Amenable to bone marrow evaluations and peripheral blood sampling during the study.
12. Must have discontinued ET therapy at least 1 week (4 weeks for interferon) prior to study drug initiation.
13. Women of childbearing potential (WOCBP) and fertile men (see Section 6.1) must agree to use an approved method of contraception from Screening until 14 days* after last IMG-7289 dose. Methods of contraception include: estrogen and progestogen combined hormonal contraception which inhibits ovulation; progestogen-only hormonal contraception associated with inhibition of ovulation; intrauterine device (IUD); bilateral tubal occlusion; vasectomized partner in a monogamous sexual relationship (vasectomy or tubal ligation at least six months prior to dosing); and, complete sexual abstinence (defined in Section 6.1). Males with a pregnant partner must agree to use a condom to avoid exposure to the developing child. Patients practicing abstinence must agree to use an approved method of contraception should they become sexually active during the study.

*The risk of embryofetal toxicity is fully mitigated by 28 days which is >10 half-lives of the drug at the doses used in this study.

Exclusion Criteria

1. Hemoglobin < 10 g/dL prior to dosing on Day 1.
2. Transfusion dependency, defined as requiring 2 or more units of pack red blood cells per month for more than 3 months, or a hemoglobin level of ≤ 8 g/dL in the preceding 8 weeks before the start of dosing.
3. Eastern Cooperative Oncology Group (ECOG) questionnaire score of 3 or greater at Screening.
4. History of splenectomy.

5. Has undergone major surgery ≤ 4 weeks prior to starting study drug or has not recovered from side effects of such surgery.
6. Unresolved treatment related toxicities from prior therapies (unless resolved to \leq Grade 1).
7. Uncontrolled active infection.
8. Known positive for HIV if not well-controlled (i.e., undetectable viral load) or infectious hepatitis, type A, B or C.

Note for Italy: Active infection with hepatitis A virus, B virus (positive hepatitis B surface antigen; **note:** positive hepatitis B surface antibody and positive hepatitis B core antibody are not exclusionary provided disease is not active, which should be clearly documented in the patient's medical history) or C virus (patients with positive hepatitis C antibody result would require confirmation of active disease with a positive hepatitis C polymerase chain reaction (PCR) test), seropositivity for human immunodeficiency virus (HIV).

9. Current use of monoamine oxidase A and B inhibitors (MAOIs).
10. Evidence at the time of screening of increased risk of bleeding, including any of the following:
 - Activated partial thromboplastin time (aPTT) > 1.3 x the upper limit of normal
 - International normalized ratio (INR) > 1.3 x the local upper limit of normal
 - History of severe thrombocytopenia or platelet dysfunction unrelated to a myeloproliferative disorder or its treatment
 - Known bleeding disorder (e.g., dysfibrinogenaemia, factor IX deficiency, hemophilia, Von Willebrand's disorder, Disseminated Intravascular Coagulation [DIC], fibrinogen deficiency, or other clotting factor deficiency)
11. Evidence at the time of Screening of significant renal or hepatic insufficiency (unless due to hemolysis, or leukemic infiltration) as defined by any of the following local lab parameters:
 - Calculated glomerular filtration rate (GFR; using the Cockcroft-Gault equation) < 40 mL/min or serum creatinine > 1.5 x the local upper limit of normal
 - Aspartate transaminase (AST) or alanine aminotransferase (ALT) ≥ 2 x the local upper limit of normal
12. Current use of a prohibited medication (e.g., romiplostim) or expected to require any of these medications during treatment with the investigational drug.
13. Known immediate or delayed hypersensitivity reaction or idiosyncrasy to drugs chemically related to IMG-7289 or LSD1 inhibitors (i.e., monoamine oxidase inhibitors; MAOIs) that contraindicates their participation.
14. History of any illness/impairment of gastrointestinal (GI) function that might interfere with drug absorption (e.g., chronic diarrhea), confound the study results or pose an additional risk to the patient by participation in the study; patients with gastric bypass surgery.

15. Use of an investigational agent within less than 14 days, or the equivalent of at least 7 half-lives of that agent, whichever is the longer, prior to the study Day 1.
16. Females who are pregnant or breastfeeding or plan to become pregnant or breastfeed during the study.
17. A concurrent second active and non-stable malignancy (patients with a concurrent second active but stable malignancy, such as non-melanoma skin cancers, are eligible).

GUIDELINES: These guidelines are for use by the Investigator, study staff and patient to safeguard patient safety while maintaining data integrity.

1. In general, supportive care (transfusions, administration of anti-fungals, etc.) should be maintained in accordance with institutional policy.
2. Patients taking medications with the potential to induce or inhibit CYP_{3A4} or CYP_{2D6} should be monitored closely for potential effects of co-administration; particular attention should be given to anti-infectives in the azole class.
3. Cessation of IMG-7289 is invariably associated with a rebound in thrombopoiesis and platelet counts may easily exceed the baseline value. When IMG-7289 is discontinued, the platelet count should be monitored closely and an alternative cyto-reductive therapy to lower platelets should commence within 24-48 hours.

CCI

Management of Study Toxicities: Adverse event intensity will be evaluated using the National Cancer Institute (NCI) Common Terminology Criteria for Adverse Events (CTCAE) version 5, published 27 November 2017. Please refer to Section 8.2 for additional detail on management of study toxicities, including reduction of the starting dose based on dose limiting toxicity (DLT).

Definitions:

Hematologic Toxicity: Hematologic values outside of the normal reference range are inherent features of MPNs and are expected effects of many therapeutic attempts to manage these diseases. The effects of IMG-7289 on normal myeloid hematopoiesis observed in non-clinical and clinical studies are expected; these are pharmacodynamic effects of LSD1 inhibition by IMG-7289, thus are not regarded as adverse. These events, with the exceptions below, will not be considered DLTs.

Dose limiting toxicity (DLT): Any one of the following AEs that occurs through Day 7 of the Initial Treatment Period and is considered by the Investigator to be possibly, probably or definitely related to IMG-7289:

- Any Grade 2 or above thrombocytopenia associated with clinically significant bleeding*
- Any Grade 3 or above thrombocytopenia;
- Any Grade 4 or 5 non-hematologic adverse event;
- Any Grade 3 or above non-hematologic adverse event with failure to recover to Grade 2 within 7 days of drug cessation, with the following exceptions:
 - nausea, vomiting or diarrhea that responds to standard medical care
 - aesthenia lasting less than 14 days
- Any Grade 3 electrolyte abnormality unrelated to the underlying malignancy (for example, hyperkalemia *is* related to thrombocytosis and would therefore not qualify as DLT) and persisting greater than 24 hours.

*Clinically significant bleeding is defined as an event that is life-threatening, cannot be controlled and/or results in hemodynamic instability.

Patients who experience a DLT may have their dose adjusted downward if the Medical Monitor and Principal Investigator (PI) deem it safe for the patient to continue on IMG-7289. Any patient that experiences DLT that results in discontinuation of IMG-7289 therapy may begin alternative cytoreductive therapy to lower platelets within 24-48 hours.

Please contact the Imago medical monitor to discuss IMG-7289 dose modifications for the management of clinically significant changes in platelets, neutrophil counts, or other hematologic parameters.

Stopping Rules:

IMG-7289 will be discontinued in the event of the following:

- Post DLT, the Medical Monitor and Principal Investigator deem it unsafe for the patient to continue on IMG-7289.
- Post dose reduction due to DLT, the patient fails to demonstrate significant improvement within 21 days.
- Post temporary interruption of IMG-7289 due to platelet counts below 50 k/ μ L ($50 \times 10^9/L$), the patient's platelet counts don't return to >150 k/ μ L ($150 \times 10^9/L$) within 21 days.

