6.6 Prohibited Medications

Please consult the Medical Monitor with any questions pertaining to prohibited medications.

1. All cytotoxic agents, including standard-of-care therapies for ET
2. All hematopoietic growth factors: romiplostim, eltrombopag, granulocyte and granulocyte-macrophage colony stimulating factor (G-CSF and GM-CSF) and erythropoietin (EPO)
3. Monoamine oxidase A and B inhibitors
4. Anticoagulant and nonsteroidal anti-inflammatory drug (NSAID; including aspirin) use are only prohibited in patients when their platelet count is < 50 k/ μ L (50×10^9 /L)

CCI

CCI [REDACTED]

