11.2 Adverse Events

The Investigator is responsible for monitoring the safety of patients who have enrolled in the study and for accurately documenting and reporting information as described in this section. Patients will be instructed to report to the Investigator any AE that they experience. Investigators will ask about the occurrence of AEs at each visit. Investigators are required to document all AEs occurring during the clinical study, commencing with the first dose of IMG-7289 through to the End of Study Visit (scheduled at 14 days post last IMG-7289 dose). Adverse event recording will continue for patients who discontinue study treatment early but remain in follow-up, until their End of Treatment, Pre-End of Study and End of Study Visits have been completed.

Note: Any medical event which occurs from the time of Informed Consent but prior to dosing with IMG-7289 must still be documented in the patient's medical notes and will be recorded on the appropriate medical history eCRF pages. **In the UK only**, serious AEs (SAEs) will be recorded from time of consent.

Adverse events will be recorded on designated eCRF pages. Each AE is to be characterised (i.e., verbatim term) and information provided regarding its seriousness, start and stop dates, intensity, outcome, and causal relationship with the study drug.

An AE is any undesirable physical, psychological or behavioral effect experienced by a patient during participation in an investigational study, in conjunction with the use of the drug or biologic, whether or not product-related. This includes any untoward signs or symptoms experienced by the patient from the time of first dose with IMG-7289 until completion of the study.

Adverse events may include, but are not limited to:

- Subjective or objective symptoms spontaneously offered by the patient and/or observed by the Investigator or medical staff
- Findings at physical examinations
- Laboratory abnormalities of clinical significance

It is important Investigators record accurate AE terms in the eCRFs. Wherever possible, a specific disease or syndrome rather than individual associated signs, symptoms or laboratory parameter will be identified by the Investigator and recorded in the eCRF. However, if an observed or reported sign, symptom or laboratory parameter is not considered a component of a specific disease or syndrome by the Investigator, or is atypical, it should be recorded as a separate AE in the eCRF.

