Disease signs, symptoms, and/or laboratory abnormalities already existing prior to the use of the investigational product are not considered AEs after treatment unless they reoccur after the patient has recovered from the preexisting condition or in the opinion of the Investigator they represent a clinically significant exacerbation in intensity or frequency.

Clinical significance is defined as any variation in signs, symptoms, or testing that has medical relevance and may result in an alteration in medical care. The Investigator will continue to monitor the patient until the assessment returns to Baseline or until the Investigator determines that follow-up is no longer medically necessary.

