11.2.2 Adverse Event Relatedness

The Investigator will make a judgment regarding whether or not, in his/her opinion, the AE was related to study drug. The Investigator will also evaluate any changes in laboratory values, make a determination as to whether the change is clinically significant, and whether or not the change(s) were related to study drug. However, even if the Investigator feels there is no relationship to the study drug, the AE or clinically significant laboratory abnormality MUST be recorded in the eCRF. Below are guidelines for relationship assessment:

- Unrelated: There was no relationship of the adverse event to the use of the drug or biologic. This may include, but is not limited, to the adverse experience being an expected outcome of a previously existing or concurrent disease, concomitant medication or procedure the subject experienced during their treatment period.
- Remote/Unlikely: Adverse events which are judged probably not related to the drug or biologic.
- Possible: There was no clear relationship of the adverse event to the use of the drug or biologic; however, one cannot definitively conclude that there was no relationship.
- Probable: While a clear relationship to the drug or biologic cannot be established, the event is associated with an expected adverse event (per the current Investigator Brochure or SAB findings) or there is no other medical condition or intervention which would explain the occurrence of such an experience.
- Definite: The relationship of the use of the drug or biologic to the experience is considered definitively established.

If a causal relationship is considered probable, possible, or definite by the Investigator or Sponsor (dependent on the regional reporting requirements), the AE is considered to be “related” for purposes of regulatory reporting. If a causal relationship is considered remote/unlikely or unrelated, the AE is considered “unrelated” for purposes of regulatory reporting.

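### The synopsis classes expected drug effects on blood counts as not adverse, while Sections 11.2 and 11.2.2 require clinically significant laboratory abnormalities to be recorded; outside the narrow DLT exception, TEAE tables could understate cytopenias

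*Protocol*

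**What the plan says.** **Protocol Section 2 (Synopsis), Hematologic Toxicity.** The drug's effects on normal myeloid hematopoiesis seen in earlier studies are called expected, and "these are pharmacodynamic effects of LSD1 inhibition by IMG-7289, thus are not regarded as adverse". The next sentence reads: "These events, with the exceptions below, will not be considered DLTs". The DLT list that follows is introduced as a list of AEs. Its blood-count items are Grade 3 or higher thrombocytopenia, and Grade 2 or higher thrombocytopenia with clinically significant bleeding. The window ends on Day 7 here and on Day 8 in Section 8.2.2.

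**Protocol Sections 11.2 and 11.2.2.** The examples of AEs include "Laboratory abnormalities of clinical significance". Clinical significance is defined as "any variation in signs, symptoms, or testing that has medical relevance and may result in an alteration in medical care". Section 11.2.2 adds that, even where the investigator sees no link to study drug, "the AE or clinically significant laboratory abnormality MUST be recorded in the eCRF". Neither section exempts expected or pharmacodynamic effects. The only exemption is for abnormalities present before treatment, and it lapses if they recur after recovery or worsen to a clinically significant degree.

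**Analysis.** Safety and tolerability is a primary objective, assessed through AEs together with laboratory values and examinations (Protocol 12.4.1). SAP 6.4.1 tabulates treatment-emergent AEs, including related, serious, DLT, leading-to-withdrawal and maximum-severity tables. SAP 6.4.4 summarises laboratory values separately, with shift tables by normal range.

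**The concern.** The two parts of the protocol reason in opposite directions. In the synopsis, being expected takes an effect on blood counts out of the adverse category. In Section 11 what matters is whether the change may alter care, and expectedness plays no part. An investigator with a clinically significant neutropenia or a late thrombocytopenia can find support in the protocol for recording it and for not recording it.

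The TEAE tables can count only what sites enter. If some sites omit these events, the tables lose their grade, seriousness, relatedness and any link to drug withdrawal. The serious-event table inherits the gap, because Section 11.2.3 defines an SAE as a kind of AE. The affected events are not peripheral: Section 3.5 names severe thrombocytopenia as the greatest clinical risk. With approximately 25 sites planned and no by-site analyses (SAP 6.1.3), differing practice would be hard to see in the planned outputs.

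**Working it through.** The plan gives no figure to reproduce, so the check is a comparison of the two rules by type of event.

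| Event, judged clinically significant | Synopsis | Sections 11.2 and 11.2.2 | Result |
|---|---|---|---|
| Related thrombocytopenia on the DLT list, inside the window | A DLT, listed among AEs | Recordable AE | Agree |
| Thrombocytopenia after the window | Not adverse | Recordable AE | Conflict |
| Neutropenia, any time | Not adverse; no DLT item | Recordable AE | Conflict |
| Anaemia, any time | Not adverse; no DLT item | Recordable AE | Conflict |

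Red cells belong in the table because Section 3.5 counts them among the myeloid lineages that need LSD1 activity, while calling red-cell production the least sensitive.

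**How far the exception reaches.** Read generously, as limiting the word adverse and not only DLT status, the exception covers this share of the ITP:

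- Day 7 wording: 7/169 = 4.1%, leaving 162/169 = 95.9%.
- Day 8 wording: 8/169 = 4.7%, leaving 161/169 = 95.3%.

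Both windows close before Day 15, the first listed visit after Day 1 (Section 5.1.1). The whole ATP lies outside them.

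**A case that meets both rules.** Take a platelet count below 50 k/µL after the DLT window.

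1. It is an extreme form of an expected effect. The synopsis reports dose-dependent falls in platelets in earlier patients, and Section 3.5 calls platelet production the more sensitive lineage. The synopsis sentence therefore applies.
2. It alters care. The Stopping Rules begin one criterion with "Post temporary interruption of IMG-7289 due to platelet counts below 50" k/µL, and Section 6.6 prohibits anticoagulants and NSAIDs below that count. The Section 11.2 definition of clinical significance is met.
3. The pre-existing-abnormality exemption cannot apply, because inclusion criterion 5 requires "Platelet count > 450" k/µL before dosing on Day 1.

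The same count is thus not adverse under one rule and must be recorded under the other.

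**Neutrophils.** The synopsis asks sites to contact the medical monitor about dose modification for clinically significant changes in neutrophil counts as well as platelets. It therefore foresees altered care, which again meets the definition. Entry allows an ANC as low as 0.5 × 10^9/L, so some low counts will be pre-existing; a clinically significant worsening from there is still recordable under Section 11.2.

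**What is lost and what remains.** Omitted events lower the TEAE counts. They do not remove the laboratory results, which still enter the SAP 6.4.4 summaries and shift tables and the out-of-range summary planned in the protocol.

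**The case against.** The best defence is that the synopsis sentence is only about DLTs. It stands under the definitions for managing toxicities, the next sentence gives DLT classification as its purpose, and the list that follows treats severe thrombocytopenia as an AE. Other text points the same way: Section 8.2 speaks of expected toxicities, and Section 11.2.2 uses an expected adverse event as a ground for rating causality as probable. Section 11 is also where a site would look for recording instructions, and the synopsis sentence does not mention the eCRF. Finally, the synopsis sends readers to Section 8.2 for detail, and the text between 8.2 and 8.2.2 is blacked out and may contain the missing limit.

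Much of this stands. The DLT-only reading is plausible and may be what was meant, and hidden text cannot be counted as absent. But the visible sentence says not adverse, which is wider than not a DLT, and the exception is attached to the second idea only. A clarification in Section 8.2 would still leave the synopsis saying something different.

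The consequence is also bounded. Haematology is taken at every visit, laboratory values are part of the primary safety assessment, and the Safety Advisory Board reviews safety parameters at least quarterly. Falling counts would not go unseen.

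**Conclusion.** The inconsistency is real and should be corrected. Neutropenia, anaemia and thrombocytopenia after the DLT window are subject to conflicting recording rules, and any resulting error would understate cytopenias in the TEAE tables. The size cannot be computed: the visible documents give no cytopenia rates and do not show how sites read the sentence. The conclusion assumes that at least some sites take it literally and that the redacted part of Section 8.2 does not already settle the matter.

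Three stronger readings are tempting and are not supported:

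- **That the synopsis exempts all blood-count effects without any limit.** The DLT exception and the DLT context are a limit, though a narrow one.
- **That the trial would hide cytopenias.** The laboratory outputs would still show the counts; the gap is in AE grade, seriousness, relatedness and withdrawal.
- **That the SAP has no grade-based laboratory tables.** SAP 6.4.4 is heavily redacted and may contain them.

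The Day 7 and Day 8 ends of the DLT window are a separate contradiction, and those two sections must also be reconciled.

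**What to change.** **Protocol.** Reconcile the Hematologic Toxicity text in the synopsis with Section 11.2, and do the same in the redacted part of Section 8.2 if it repeats the sentence. Confine the sentence to DLT classification by removing the clause that says these effects are not regarded as adverse. Add that a cytopenia meeting the Section 11.2 definition of clinical significance is recorded and CTCAE-graded as an AE even when it is an expected effect of the drug. This concerns recording only and changes no dosing or management rule.

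**SAP, optional.** Only if the redacted part of Section 6.4.4 does not already do so, tabulate baseline against worst post-baseline CTCAE grade for platelets, neutrophils and hemoglobin. Name unscheduled results explicitly, because Section 6.1.1.2 sends them to listings unless an analysis section says otherwise. This would show severity whatever sites entered as AEs, but the recording conflict can be resolved without it.

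**Cost.** One amended passage in the protocol, a short clarification to sites and, if adopted, one set of tables from data already collected. The AE profile may look less favourable.
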